3 SCHEDULE OF ASSESSMENTS

Schedules of assessments are in Table 3-1 (surgical subjects), Table 3-2 (surgical subjects), Table 3-3 (non-surgical subjects), and Table 3-4 (all subjects).

	Day -28 to Day -1	Day 1	Comments		
Event/Assessment ^a	Screening	Pre-procedure			
Informed consent	X		Must be obtained before performing any study-related procedures. Remote consent may be used if permitted by local regulations; Section 13.2.3.		
Clinic or home health visit	Х		Subjects will have the option to complete this visit in the clinic or to have a home health visit. Home health visits are only an option if permitted by local regulations; Section 9.1.1.		
Telemedicine video conference or telephone contact	(X)		A consultation between the subject and investigator or qualified delegate (LIP) must be performed within 2 business days after the home health visit (must be within screening window) and may also include a separate follow- up with the study coordinator. Required only for subjects who have a home health visit; not required for subjects who have a clinic visit; Section 9.1.6.		
Admission for surgery (e.g., hospital or ambulatory surgical center)		Х	Upon completion of pre-procedure eligibility assessments; Section 8.		
Demographics	Х		Section 11.1		
Medical and surgical history	Х		Section 11.1		
History of drug and alcohol use	Х		Section 8.2		
Vital signs	Х	Х	Vital signs will be collected after the subject has been at rest (seated or supine) for at least 5 minutes and before any 12-lead ECG assessment or blood sampling; Section 11.5.3.		
Standard 12-lead ECG	Х	Х	Performed in triplicate after the subject has been at rest (supine) for at least 5 minutes; 12-lead ECGs will be done after taking vital signs and before any procedures that may affect heart rate (e.g., blood sampling); Section 11.5.4.		
PE	X	(X)	Section 11.5.3 Screening Visit: A complete PE will be performed if the visit occurs in clinic. An abbreviated PE will be performed if the visit occurs via home health. Day 1: A complete PE will be performed only if the Screening Visit occurs via home health. Otherwise, no PE is required.		
Weight, height, and BMI	Х		Weight and height will be measured with shoes off.		
C-SSRS		Х	Section 11.5.5		
Serology (HBsAg, HCV Ab, HCV RNA, and HIV-1/HIV-2 Abs)	X		Section 11.5.2		
Serum β-hCG	X		All biologically female subjects; Section 11.5.2.		

Table 3-1Study VX22-548-107: Screening Through Admission (Surgical Subjects)

	Day -28 to Day -1	Day 1	Comments		

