Vital signs	Х	Performed after surgery completion (at least 1 hour after surgery completion is recommended) before the first dose of study drug. Vital signs will be collected after a ≥5-minute rest (seated or supine) and before any 12-lead ECG assessment or blood sampling; Section 11.5.3.				
Standard 12-lead ECG	Х	Performed after surgery completion (at least 1 hour after surgery completion is recommended) before the first dose of study drug. Standard 12-lead ECGs will be performed in triplicate after a \geq 5-minute rest (supine); these will be done after taking vital signs and before any procedures that may affect heart rate (e.g., blood sampling); Section 11.5.4.				
VRS	Х	Completed upon request for the first dose of study drug for pain relief after surgery completion; Section 9.1.2.				
NPRS	Х	Completed immediately after the VRS only if the subject's pain is rated moderate or severe on the VRS; Section 9.1.2.				
Medications review	Continuous from signing of ICF through completion of study participation	All medications taken within 14 days before the Screening Visit through completion of study participation; Section 9.4.2.				
Nonpharmacological treatment and procedures review	Continuous from signing of ICF through completion of study participation	All nonpharmacological treatments and procedures starting from the Screening Visit.				
Adverse events	Continuous from signing of ICF through completion of study participation	Section 11.5.1				

Table 3-2Study VX22-548-107: Procedure Through Treatment Assignment
(Surgical Subjects)

ICF: informed consent form; NPRS: numeric pain rating scale; VRS: verbal categorical rating scale

^a Subject must complete all Day 1 predose assessments before the first dose of study drug is administered. When assessment time points coincide, assessments will be performed in the following order: vital signs, 12-lead ECG, and blood sample collection.

	Saraaning Visit/Day 1				
	Screening Visit/Day 1	-			
Event/Assessment ^a	Screening Through Treatment Assignment	Comments			
Presents with pain at medical	X	Section 9.1			
facility (e.g., hospital, clinic, or ambulatory center)					
Informed consent	Х	Must be obtained before performing any study-related procedures; Section 13.2.3.			
Demographics	Х	Section 11.1			
Medical and surgical history	Х	Section 11.1			
History of drug and alcohol use	Х	Section 8.2			

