PGA		X			X	X	X		Recorded in the e-diary ^d ; Section 11.4.1. Subjects should still complete the PGA even if the specified dose is not taken. Day 2: To be completed after the third study drug dose (approximately 24 hours after the first dose). Day 7: Completed after the first study drug dose on Study Day 7 (whether or not this coincides with the date of the Day 7 Visit). Day 14 or EDV: Completed after final study drug dose for subjects still taking study drug on Day 14. Subjects who have discontinued or completed study drug treatment should complete the PGA at home within approximately 24 hours after the last (or presumed last) dose of study drug rather than waiting for their scheduled visit.
Vital signs			X (postdose) ^b		Х	х	Х	Х	Vital signs will be collected after a \geq 5-minute rest (seated or supine) and before any 12-lead ECG assessment or blood sampling; Section 11.5.3.
Standard 12-lead ECG	at discharg	ours after first e or before lea ility, as applic	ving medical		X (4 hours after a dose) ^e	X (4 hours after a dose) ^{e,f}	X	(X)	Required at SFU only if any clinically significant abnormalities were noted on a prior ECG. Standard 12-lead ECGs will be performed in triplicate after a ≥5-minute rest (supine); these will be done after taking vital signs and before any procedures that may affect heart rate (e.g., blood sampling); Section 11.5.4.

Table 3-4Study VX22-548-107: Treatment Period and Safety Follow-up Visit (All Subjects)

Table 3-4Study VX22-548-107: Treatment Period and Safety Follow-up Visit (All Subjects)

Event/Assessment ^a	Day 1	Day 2	Discharge ^b	Day 4 (± 1 day)	Day 7 (± 1 day)	Day 14 (+ 3 days)	End of Dosing Visit ^c	Safety Follow-up Visit Day 28 (± 2 days)	Comments
Symptom-directed PE				As applicable					Symptom-directed PEs will occur at any time during the study if triggered by AEs or if deemed necessary by the investigator; Section 11.5.3.
Focused PE (surgical subjects only)								Х	Assessment of wound healing at the operative site; Section 11.5.3.
Complete PE								(X)	Required at SFU only if a clinical finding during the Treatment Period requires follow up, in which case the subject must have a clinic visit; Section 11.5.3.
C-SSRS			X (postdose) ^b		Х	Х	X		Section 11.5.5
Urine β-hCG						Х	Х	Х	All female subjects of childbearing potential; Section 11.5.2.
Serum chemistry			X (postdose) ^b			Х	X	(X)	Required at SFU only if a clinical finding during the Treatment

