11.5.3 Physical Examinations and Vital Signs

A PE of all body systems and vital signs assessment will be performed at screening and select study visits. At other visits, symptom-directed PEs and symptom-directed vital signs assessments

can be performed at the discretion of the investigator or healthcare provider. If the Screening Visit occurs via home health (surgical subjects only), an abbreviated PE will be performed at screening and a complete PE will be performed on Day 1.

A PE includes a review of the following systems: head, neck, and thyroid; eyes, ears, nose, and throat (EENT); respiratory; cardiovascular; lymph nodes; abdomen; skin; musculoskeletal; and neurological. Breast, anorectal, and genital examinations will be performed when medically indicated. After screening, any clinically significant abnormal findings in PEs will be reported as AEs.

The abbreviated PE will include an assessment of the following body systems: general; cardiovascular system; respiratory system; skin; and abdomen.

A focused PE of the operative site (surgical subjects only) will be performed in order to assess wound healing.

Vital signs include blood pressure (systolic and diastolic), temperature, pulse rate, respiration rate, and oxygen saturation (SpO₂). The subject will be instructed to rest (seated or supine) for at least 5 minutes before vital signs are assessed.

If there is an abnormal clinical assessment during a home visit, depending on its severity and at investigator discretion, the subject may be instructed to have a PE or other evaluation in the clinic.

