11.5.4 Electrocardiograms

Standard 12-lead ECGs will be performed in triplicate using a machine with printout. Additional standard 12-lead ECGs will be performed at any other time if clinically indicated. The performance of all ECGs will adhere to the following guidelines:

- The ECG will be done before blood draws or any other procedures that may affect heart rate.
- The subject will be instructed to rest (supine) for at least 5 minutes before having an ECG.
- The test should be performed in the supine position.

The acceptable window for the 4-hour postdose ECG is \pm 30 minutes relative to the scheduled nominal time.

A printout of the ECG traces will be made for safety review by the investigator and maintained with source documentation. All traces will be centrally evaluated by a qualified cardiologist. Clinically significant ECG abnormalities occurring during the study through the Safety Follow-up Visit will be recorded as AEs.

To ensure safety of the subjects, a qualified individual at the study site will make comparisons to baseline measurements. If the median QTcF is increased by >60 msec from the baseline or the median absolute QTcF value is \geq 500 msec for any scheduled or unscheduled ECGs (performed in triplicate), 2 additional ECGs (performed in triplicate) will be performed approximately 2 to 4 minutes apart to confirm the original measurement. If the median QTcF value from either of these repeated ECGs remains above the threshold value (>60 msec from baseline or \geq 500 msec), the subject should discontinue dosing. For safety monitoring after discontinuation, a single ECG will be repeated at least hourly until QTcF values from 2 successive ECGs fall below the threshold value that triggered the repeat measurement.

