9.4.4 Vital Signs

For the treatment-emergent vital signs measurements, the observed values and change from baseline values will be summarized at each visit. The following vital signs parameters will be summarized: systolic and diastolic blood pressure (mm Hg), pulse rate (beats per minute), body temperature (°C), respiratory rate (breaths per minute), and oxygen saturation (%).

The number and percentage of subjects meeting threshold analysis criteria during the TE Period will be summarized. The threshold analysis criteria are provided in Appendix D.

In addition, a listing containing individual subject vital signs values will be provided. This listing will include data from both scheduled and unscheduled visits.

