Table 12-3 Threshold Analysis Criteria for Laboratory Tests (as applicable)

Table 12-4 Threshold Analysis Criteria for ECGs

Parameter	Threshold Analysis	Comments
HR	Bradycardia <50 bpm <45 bpm Decrease from baseline ≥10 bpm Decrease from baseline ≥20 bpm <50 bpm and decrease from baseline ≥10 bpm <50 bpm and decrease from baseline ≥20 bpm	Per HV grade 2, 3, plus shift change
	Tachycardia >100 bpm >115 bpm >130 bpm Increase from baseline ≥10 bpm Increase from baseline ≥20 bpm >100 bpm and increase from baseline ≥10 bpm >100 bpm and increase from baseline ≥20 bpm	Per HV grade 1, 2, 3, plus shift change
PR	≥240 ms ≥300 ms ≥200 ms and increase from baseline ≥40 ms ≥200 ms and increase from baseline ≥100 ms	
QRS	>110 ms >160 ms Increase from baseline ≥20 ms Increase from baseline ≥40 ms	
QTc	>450 to <500ms (Male) or >470 to <500ms (Fema ≥500 ms Increase from baseline Increase from baseline >10 ms Increase from baseline >20 ms Increase from baseline >40 ms Increase from baseline >60 ms	ale) To be applied to any kind of QT correction formula.

Parameter	Threshold Analysis	Comments
Pulse Rate	Same as above in ECG category	
SBP increased	>140 mmHg	
	>160 mmHg	
	>10 mmHg increase from baseline	
	>20 mmHg increase from baseline	
	>140 mmHg & >10 mmHg increase from baseline	
	>140 mmHg & >20 mmHg increase from baseline	
	>160 mmHg & >10 mmHg increase from baseline	
	>160 mmHg & >20 mmHg increase from baseline	
SBP decrease	<90 mmHg	Per HV grade 1, 3, plus shift change
	<80 mmHg	
	>10 mmHg decrease from baseline	
	>20 mmHg decrease from baseline	
	<90 mmHg and >10 mmHg decrease from baseline	
	<90 mmHg and >20 mmHg decrease from baseline	
	<80 mmHg and >10 mmHg decrease from baseline	
	<80 mmHg and >20 mmHg decrease from baseline	
DBP increased	>90 mmHg	
	>100 mmHg	
	>5 mmHg increase from baseline	
	>10 mmHg increase from baseline	
	>90 mmHg and >5 mmHg increase from baseline	
	>90 mmHg and >10 mmHg increase from baseline	
	>100 mmHg and >5 mmHg increase from baseline	
	>100 mmHg and >10 mmHg increase from baseline	
DBP decreased	<60 mmHg	
	<45 mmHg	
	>5 mmHg decrease from baseline	
	>10 mmHg decrease from baseline	
	<60 mmHg and >5 mmHg decrease from baseline	
	<60 mmHg and >10 mmHg decrease from baseline	
	<45 mmHg and >5 mmHg decrease from baseline	
	<45 mmHg and >10 mmHg decrease from baseline	
Oxygen saturation	<88%	
decreased	<95% and decrease from baseline $>5%$ of absolute	
	oxygen saturation	

 Table 12-5
 Threshold Analysis Criteria for Vital Signs

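### Vital signs may be taken seated or supine at every assessment, and the SAP computes blood-pressure change from baseline without regard to position, so a change of position could add to or mask a change

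*Protocol*

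**What the plan says.** Every scheduled vital-sign assessment offers a choice of position.

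- Protocol Section 11.5.3: "The subject will be instructed to rest (seated or supine) for at least 5 minutes before vital signs are assessed".
- Table 3-1 (surgical screening and pre-procedure) and Table 3-3 (non-surgical Day 1): "Vital signs will be collected after the subject has been at rest (seated or supine) for at least 5 minutes".
- Table 3-2 (surgical predose) and Table 3-4 (Discharge, Day 7, Day 14 or End of Dosing, Safety Follow-up): "Vital signs will be collected after a ≥5-minute rest (seated or supine) and before any 12-lead ECG assessment or blood sampling".

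The surgical predose reading is "Performed after surgery completion (at least 1 hour after surgery completion is recommended) before the first dose of study drug". For ECGs the protocol does fix position, in Section 11.5.4: "The test should be performed in the supine position".

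The SAP takes as baseline the last non-missing value before the first dose (Section 9.1), with no condition on position. For vital signs, Section 9.4.4 states that "the observed values and change from baseline values will be summarized at each visit", and it counts subjects who meet a threshold at any time in the treatment-emergent period. Table 12-5 sets change thresholds of >10 and >20 mmHg systolic and >5 and >10 mmHg diastolic, up and down; the smallest upward one reads ">5 mmHg increase from baseline". Pulse uses the ECG heart-rate criteria of Table 12-4, with changes of 10 and 20 bpm. Vital signs are part of the primary endpoint, and there is no control arm.

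**The concern.** If a subject is measured in one position at baseline and in the other later, the computed change contains the difference between positions as well as anything due to VX-548. A concurrent control group would carry the same difference and allow it to be subtracted. Here nothing does that.

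A change of setting is built into the design. The surgical baseline is taken after surgery on Day 1, whereas the Day 7 and Safety Follow-up readings may be taken in the clinic or at home. A shift that runs mainly one way would raise one set of threshold counts and lower the opposite set, so it could suggest a blood-pressure effect or conceal one. The smaller thresholds are the most exposed, because a few mmHg is enough to cross them.

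**Working it through.** **The plan's own figure.** The only computed design figure is the chance of seeing at least one AE in 250 subjects: 1 − 0.99^250 = 91.9% (stated 92%) and 1 − 0.98^250 = 99.4% (stated 99%). Both reproduce. Neither depends on body position, and the documents give no figure that does, so what follows is an illustration.

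**Inputs from the documents.** Diastolic change threshold >5 mmHg (Table 12-5). A count of subjects with any qualifying value over the treatment-emergent period (SAP 9.4.4). Up to four post-baseline readings: Discharge, Day 7, Day 14 or End of Dosing, and Safety Follow-up (Table 3-4).

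**Inputs that are assumptions.** No drug effect. Independent normal readings with SD 7 mmHg. A position shift of 0, 3, 5 or 8 mmHg. The share of subjects who switch position, and the visits at which they do.

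**Formula.** Let b be the baseline deviation and s_j the shift at visit j. The share with at least one rise >5 mmHg is 1 − E_b[ Π_j Φ((5 + b − s_j)/7) ], and falls are computed in the mirror-image way. One check needs no computer. With a 5 mmHg shift at all four visits, a rise >5 mmHg occurs whenever any of four exchangeable readings exceeds the baseline reading, so the share is 4/5 = 80%, whatever the SD.

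**Two scenarios.** A: half the subjects switch at the three visits after Discharge and the other half never do. B: every subject is shifted at all four visits.

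| Shift (mmHg) | Rise >5, A | Rise >5, B | Fall >5, A | Fall >5, B |
|---|---|---|---|---|
| 0 | 60% | 60% | 60% | 60% |
| 3 | 65% | 73% | 55% | 46% |
| 5 | 68% | 80% | 52% | 37% |
| 8 | 73% | 88% | 49% | 25% |

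Each scenario A entry averages switchers and non-switchers. For rises at 5 mmHg: (76.9% + 59.9%)/2 = 68.4%.

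**Sensitivity to SD.** For the 5 mmHg shift, scenario A moves rises from 51% to 63% at SD 5 and from 65% to 71% at SD 9.

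**Sensitivity to visit count.** Four readings is the maximum. Discharge readings apply to surgical subjects and admitted non-surgical subjects only (Table 3-4, footnote b). The End of Dosing Visit replaces Day 14, and also Day 7 if it falls within or before that window (footnote c). With three or two readings the no-shift share is 54% or 45%, and a 5 mmHg shift of every subject at every visit takes it to 75% or 67%.

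**Mean change.** At a visit where half the subjects have switched, the mean moves by 0.5 × 3 = 1.5 to 0.5 × 8 = 4 mmHg.

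**The case against.** The case against giving this much weight is substantial.

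- **All the drivers are assumed.** A reader might infer that baseline is supine, later readings are seated, and the results will therefore be biased in one direction. The documents do not support that. They permit mixed positions; they do not report which are used. This objection stands.
- **The schedule partly works against the feared pattern.** Vital signs come just before a supine ECG predose on Day 1, at Day 7 and at Day 14 or End of Dosing, so supine is convenient at both ends of the comparison. Safety Follow-up is the one post-baseline visit with no routine ECG. This makes systematic switching less likely but does not rule it out.
- **The large figures are a worst case.** A reader might take 73%, 80% and 88% as the expected distortion. They arise only if every subject shifts at all four visits, Discharge included.
- **Pulse is partly protected.** Supine ECG heart rate is analysed against the same thresholds. Pulse and ECG counts may differ anyway, because SAP 9.4.3 uses all reported ECG replicates for thresholds. Blood pressure has no such back-up.
- **The consequence is limited.** The analyses are descriptive, with no hypothesis test. Investigators record clinically significant worsening as AEs. Table 12-5 also has larger, absolute and combined criteria. In the illustration 60% cross the 5 mmHg diastolic threshold by noise alone, so that count says little even with position fixed. All this stands and lowers the priority.
- **Other confounders remain.** Recovery from surgery and anesthesia, and falling pain, also move blood pressure after baseline.
- **The eCRF is not among the documents.** It cannot be said that position goes unrecorded, only that neither the protocol nor the SAP asks for it.

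**Conclusion.** The point holds in a limited form. The protocol leaves position open at every vital-sign assessment, and the SAP computes change and threshold counts as if position did not matter. In a single-arm study, a change of position could add to or mask a blood-pressure change.

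Under the stated assumptions, half the subjects shifting after Discharge raises the share with any diastolic rise >5 mmHg by about 5 to 13 percentage points (65 − 60 to 73 − 60) and lowers the share with a fall by about 5 to 11 (60 − 55 to 60 − 49). These figures show sensitivity and do not predict what this trial will observe. No sample-size figure or test is affected. This is a low-priority standardisation point, worth making because this source of variation can be removed by wording while the others cannot.

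**What to change.** In Section 11.5.3 and Tables 3-1 to 3-4, replace *(seated or supine)* with *supine*, or with *in the same position as the Day 1 predose measurement*. Record position at each reading if the eCRF does not already do so. In SAP Section 9.4.4, flag changes computed across different positions, or summarise them separately, wherever position is known. If data have already been collected, the SAP step is still useful for readings whose source records show position.

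The cost is a wording change, possibly one eCRF field, and a footnote or short supplementary table. If supine is chosen, the rest needed for the ECG serves both measurements at the visits where an ECG follows. The small downside is a 5-minute supine rest at Safety Follow-up, where an ECG is not routine.

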11.5.4 Electrocardiograms

Standard 12-lead ECGs will be performed in triplicate using a machine with printout. Additional standard 12-lead ECGs will be performed at any other time if clinically indicated. The performance of all ECGs will adhere to the following guidelines:

- The ECG will be done before blood draws or any other procedures that may affect heart rate.
- The subject will be instructed to rest (supine) for at least 5 minutes before having an ECG.
- The test should be performed in the supine position.

The acceptable window for the 4-hour postdose ECG is \pm 30 minutes relative to the scheduled nominal time.

A printout of the ECG traces will be made for safety review by the investigator and maintained with source documentation. All traces will be centrally evaluated by a qualified cardiologist. Clinically significant ECG abnormalities occurring during the study through the Safety Follow-up Visit will be recorded as AEs.

To ensure safety of the subjects, a qualified individual at the study site will make comparisons to baseline measurements. If the median QTcF is increased by >60 msec from the baseline or the median absolute QTcF value is \geq 500 msec for any scheduled or unscheduled ECGs (performed in triplicate), 2 additional ECGs (performed in triplicate) will be performed approximately 2 to 4 minutes apart to confirm the original measurement. If the median QTcF value from either of these repeated ECGs remains above the threshold value (>60 msec from baseline or \geq 500 msec), the subject should discontinue dosing. For safety monitoring after discontinuation, a single ECG will be repeated at least hourly until QTcF values from 2 successive ECGs fall below the threshold value that triggered the repeat measurement.

